Appendix H
Algorithm on Management of Hyponatraemia

ALGORITHM ON MANAGEMENT OF HYPONATRAEMIA

If a patient experiences a serum sodium ≤ 125 mmol/L, with or without symptoms, dosing of blinded investigational product will be interrupted. A repeat serum sodium concentration will be drawn within 3 days of the receipt of the result.

- If the repeat sodium concentration within 3 days is ≥ 130 mmol/L

Investigational product may be restarted unless otherwise contraindicated. Serum sodium will be rechecked in 7 days after restarting the investigational product.
 - If the repeat sodium concentration within 7 days of restarting the investigational product is < 130 mmol/L, investigational product will be discontinued. Patients will have an end of treatment visit and a follow-up visit three weeks after discontinuation of investigational product as specified in section 5.8.1 in the CSP.
 - If the repeat sodium concentration within 7 days of restarting the investigational product is ≥ 130 mmol/L, further management should be based on composite of sodium concentration, clinical assessment of the patient and an evaluation of underlying cause of hyponatraemia.
- If the repeat sodium concentration within 3 days is < 130 mmol/L

If there is **no** suspected new, temporary, and reversible cause of hyponatraemia based on clinical assessment (other than investigational product), investigational product will be discontinued. Patients will have an end of treatment visit and a follow-up visit three weeks after discontinuation of investigational product as specified in section 5.8.1 in the CSP.

If there is a suspected new, temporary, and reversible cause of hyponatraemia based on clinical assessment (other than investigational product), investigational product will continue to be interrupted. The suspected cause of hyponatraemia should be identified and corrected. The serum sodium will be rechecked in another 7 days.
 - If the repeat sodium concentration within 7 days is < 130 mmol/L, investigational product will be discontinued. Patients will have an end of treatment visit and a follow-up visit three weeks after discontinuation of investigational product as specified in section 5.8.1 in the CSP.

- If the repeat sodium level concentration within 7 days is ≥ 130 mmol/L investigational product may be restarted unless otherwise contraindicated. Serum sodium will be rechecked in 7 days after restarting the investigational product, and further management should be based on composite of sodium concentration, clinical assessment of the patient and an evaluation of underlying cause of hyponatraemia.

For patients whose serum sodium is in the range of 126 to 129 mmol/L, the investigator's clinical judgment should apply concerning whether such patients should be entered into this algorithm.

Clinical Study Protocol Appendix I

Drug Substance	dapagliflozin
Study Code	D1693C00005
Edition Number	1

Appendix I
Algorithm on Management of Sustained Elevated Liver Safety
Abnormalities

ALGORITHM ON MANAGEMENT OF SUSTAINED ELEVATED LIVER SAFETY ABNORMALITIES

The monitoring for liver safety will be performed using the serum levels of AST, ALT and TB (see Figure 1 algorithm flow chart).

Patients with a central laboratory ALT and/or AST >3X ULN will be scheduled for a follow-up visit within 3 days following receipt of the initial laboratory results, to obtain repeat central laboratory ALT, AST, TB and Alkaline Phosphatase (ALK-P). In the event that the repeat laboratory assessments cannot be obtained within 3 days, the Investigator is encouraged to discuss possible alternatives with the Sponsor. Patients should remain on study medication until confirmatory results are obtained, unless otherwise contraindicated.

- **If the repeat ALT and AST are $\leq 3X$ ULN**, patient should continue double-blind treatment according to their original visit schedule unless otherwise contraindicated.
- **If the repeat ALT and/or AST are $>3X$ ULN but $\leq 8X$ ULN and TB $\leq 1.5X$ ULN**, the patient's medical history, including details of risk factors for liver diseases, should be evaluated for potential underlying aetiologies. In addition, specialized blood sampling will be performed to evaluate liver function as well as identify potential causes of laboratory elevation(s). The Investigator should continue to monitor the patient's liver tests every 3 days following receipt of the prior laboratory results until the ALT and AST are $\leq 2X$ ULN or until ALT and AST are at or below baseline levels. The frequency of retesting can decrease to once a week or less if abnormalities stabilize and the patient is asymptomatic. Patients should remain on study medication unless confirmatory results indicate that a criterion for discontinuation has been met or continuing study medication would be otherwise contraindicated.

Patients must be discontinued from the study if an initial and repeat confirmatory laboratory tests meet any of the following criteria:

- ALT and/or AST are >3 x ULN and TB >1.5 x ULN
- ALT and/or AST are >5 x ULN for ≥ 14 consecutive days, at any time after initial confirmatory results
- ALT and/or AST are >8 x ULN

In each of these situations, study medication will be discontinued, the Sponsor notified and the End of Treatment Visit performed within 3 days of the confirmed laboratory results (see Section 5.8.1). At the End of Treatment Visit, medical history including details of risk factors for liver diseases (if not previously assessed) will be requested and additional blood sampling performed (**Specialized Liver Panel** and **Liver Discontinuation Panel**, see detailed below). Patient should also be scheduled for a Follow-up Visit (ie, procedures of Visit 14) 3 weeks

after discontinuation of investigational product. A referral consultation to a hepatologist or gastroenterologist (specializing in liver abnormalities) should be obtained.

Any additional tests and/or examinations should be carried out at the discretion of the Investigator. Any further investigations and laboratory results for patients with abnormal laboratory values at the Follow-up Visit should be made available to the Sponsor upon request.

Additional information, including but not limited to completion of supplemental eCRFs may be requested for certain adverse events and/or laboratory abnormalities which are reported/identified as part of the hepatic safety surveillance.

Following the End of Treatment Visit, the Investigator should continue to monitor the subject's liver tests every 3 days following receipt of the prior laboratory results until the ALT and AST are ≤ 2 x ULN or until ALT and AST are at or below baseline levels. The frequency of retesting can decrease to once a week or less if abnormalities stabilize and the subject is asymptomatic.

Guidance on Assessment of Hepatic Laboratory Abnormalities

The following is presented to assist in the evaluation and management of hepatic laboratory values. It is not intended to supplant Investigators' clinical judgment.

Patients who experience ALT and/or AST values >3 x ULN confirmed with a repeated test will have the following performed within 3 days of the confirmed laboratory results:

- AE assessment
- Physical Examination for jaundice and other signs of liver diseases
- Review of relevant risk factors and current history focusing on possible causes of the increased ALT and/or AST and/or TB, including:
 - Use of suspect concomitant medication [including over-the-counter (ie, acetaminophen/paracetamol), herbal and vitamin preparations]
 - Recent alcohol consumption or recreational drug/narcotic use
 - Recent unaccustomed physical exertion
 - Occupational or environmental exposure to hepatotoxins
 - Other conditions which may cause liver diseases or which may cause abnormal test results
- Specialized Liver Laboratory Panel (see below)

Specialized Liver Panel

For patients who are being monitored frequently as a result of confirmed AST and/or ALT >3X ULN, additional central laboratory tests will be performed within 3 days of receipt of confirmatory results. These laboratory tests will study the possible causes of the increased ALT and/or AST and/or TB, and may include, but are not limited to, the following tests:

- Hepatitis A IgM
- Hepatitis BsAg
- Hepatitis B Core Ab IgM
- Hepatitis C virus RNA
- Hepatitis C Ab
- Hepatitis E IgM
- Epstein-Barr Virus (EBV) IgM Ab
- Lactate Dehydrogenase (LDH)
- Gamma-glutamyl-transpeptidase (GGT)
- Carbohydrate deficient transferrin (CDT)
- Prothrombin time (PT/INR)
- Iron Panel - iron, ferritin, total iron binding capacity (TIBC)
- Immunology Panel including Antinuclear Antibody (ANA), Anti-Smooth Muscle Antibody (SMA) and Anti-Liver/Kidney Microsomal Antibody (Anti-LKM)
- Anti-tissue Transglutaminase Antibody

Liver Discontinuation Panel

[figure not shown]
For patients who are discontinued from the study as a result of sustained elevated liver safety abnormalities, additional central laboratory tests will be performed at the time of End of Treatment Visit. Similar to the Specialized Liver Panel, these laboratory tests will study the possible causes of the increased ALT and/or AST and/or TB, and may include, but are not limited to, the following tests:

- Cytomegalovirus (CMV) IgM Ab
- Herpes Simplex Virus (HSV) 1 and 2

- Ceruloplasmin
- Toxoplasmosis
- Alpha-1 antitrypsin

For specific details regarding the Specialized Liver Panel or the Liver Discontinuation Panel laboratory tests, refer to the Central Laboratory Manual for this study.

Figure 1 Sustained elevated liver safety abnormalities flow chart

^a In patients with repeat ALT or AST > 3x ULN but ≤ 8x ULN, only patients with TB ≤ 1.5x ULN at Step 1 should be followed according to Step 2b. Patients with an initial TB and confirmatory repeat TB > 1.5x ULN should be followed according to Step 2d.

^b Please see text above in the Appendix for details on additional assessments to be performed (AE assessment, PE, review of current medical history including focused review of current medical history including focused review of risk factors for liver diseases and collection of blood samples [specialized liver panel or liver discontinuation panel]).

^c Confirmatory repeat AST, ALT, ALK-P and TB should be obtained every 3 days following receipt of prior laboratory results, until the ALT and AST are ≤ 2x ULN or until ALT and AST are at or below baseline levels. The frequency of retesting can decrease to once a week or less if abnormalities stabilize and the patient is asymptomatic.

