5.8.1 Procedures for discontinuation of a patient from Investigational Product

A patient that decides to discontinue investigational product will always be asked about the reason(s) and the presence of any Adverse Events. If possible, the patient will undergo procedures of Visit 11 (End of Treatment Visit) as soon as possible after last intake of investigational product and will have a Follow-up Visit (Visit 12) 3 weeks after last intake of investigational product (see Table 3). Adverse Events will be followed up (See Sections 6.4.3 and 6.4.4). Patient's diaries and all investigational products should be returned by the patient.

Stop of investigational product will lead to withdrawal from the study after completion of the Follow up Visit (Visit 12).

Patients with an increased CK >10x ULN will have their investigational product temporarily stopped and undergo a repeated CK test preferably within 24 hours, but not exceeding 72 hours. If repeated CK is confirmed >10x ULN the patient should permanently discontinue study medication (in which case an Adverse Event must be reported). Otherwise investigational product may be resumed unless otherwise contraindicated.

Patients with increased liver function tests as defined in Section 5.8 under listing 16 will have repeat liver function tests within 3 days. If repeat liver function tests still are increased as outlined in Section 5.8 under listing 16, the patient should immediately permanently

discontinue study medication (in which case an Adverse Event must be reported). If repeat liver function tests still are increased but not meet criteria outlined in Section 5.8 under listing 16, the patient should continue study medications unless otherwise contraindicated.

After discontinuation of investigational product, alternative anti-hyperglycaemic treatment will be initiated according to the investigator's judgement and according to local medical practice.

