6.4.5 Laboratory safety assessment

Blood and urine samples for determination of clinical chemistry, haematology, coagulation and urinalysis will be taken at the times indicated in the Study Plan (see Table 3).

The date and time of sampling will be recorded on the laboratory requisition form. The samples will be processed by a central laboratory and results will be reported back to the clinic within 72 hours.

All samples should be taken by adequately trained study personnel and handled in accordance with instructions in the laboratory manual. Up to date reference ranges will be provided during the study and laboratory results will be compared to the laboratory standard normal ranges and flagged if they are outside the normal range. The Investigator should make an assessment of any clinically significant abnormalities in the laboratory reports. The laboratory reports should be signed, dated and retained at the study site as source data for laboratory variables.

For information on how AEs based on laboratory tests should be recorded and reported, see Section 6.4.3.

The following laboratory variables will be measured:

Table 8 Safety laboratory variables

Visit	1	2	3	4	5	6	7	8	9	10	11	12	R
Study Week	-9	-8	-2	0	4	8	16	24	32	40	52	55	
Haematology													
Haemoglobin	X			X	X	X	X	X	X	X	X	X	X
Haematocrit	X			X	X	X	X	X	X	X	X	X	X
Red blood cell count	X			X		X		X			X	X	X
White blood cell count and differential	X			X		X		X			X	X	X
Platelet count	X			X		X		X			X	X	X
Clinical chemistry (serum)													
Aspartate Aminotransferase (AST, SGOT)	X			X	X	X	X	X	X	X	X	X	X
Alanine Aminotransferase (ALT, SGPT)	X			X	X	X	X	X	X	X	X	X	X
Alkaline Phosphatase (AP)	X			X	X	X	X	X	X	X	X	X	X
Creatine Kinase (CK)	X			X	X	X	X	X	X	X	X	X	X
Total Bilirubin (TB) ^{a)}	X			X	X	X	X	X	X	X	X	X	X
Blood Urea Nitrogen (BUN)	X			X	X	X	X	X	X	X	X	X	X

Visit	1	2	3	4	5	6	7	8	9	10	11	12	R
Study Week	-9	-8	-2	0	4	8	16	24	32	40	52	55	
Electrolytes: (- Sodium - Bicarbonate - Potassium - Chloride - Calcium - Magnesium - Phosphorus)	X			X	X	X	X	X	X	X	X	X	X
Total protein	X			X		X		X			X	X	X
Albumin	X			X		X		X			X	X	X
Uric acid	X			X	X	X	X	X	X	X	X	X	X
Serum Creatinine (SCr)	X			X	X	X	X	X	X	X	X	X	X
Calculated creatinine clearance (Cockcroft- Gault formula) ^{b)}	X			X	X	X	X	X	X	X	X	X	X
Estimated Glomerular Filtration Rate (MDRD formula)	X			X	X	X	X	X	X	X	X	X	X
Serum Bone Metabolism Marker (Parathyroid Hormone (PTH) and 25 hydroxy- vitamin D)				X				X			X	X	X
FSH	X												

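### Appendix I sets no longest retest interval for a patient on study drug with ALT or AST above 5 x ULN, so the mandatory 14-day stopping criterion can be recognised late

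*Protocol*

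**What the plan says.** Appendix I, second branch, covers a repeat ALT or AST above 3 and up to 8 x ULN with bilirubin at most 1.5 x ULN.

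- **Drug continues.** "Patients should remain on study medication unless confirmatory results indicate that a criterion for discontinuation has been met", or unless continuing is otherwise contraindicated. Section 5.8.1 agrees: if the repeat values are still raised but meet no stopping criterion, "the patient should continue study medications unless otherwise contraindicated". That section gives no retest interval after the first repeat.
- **Close testing comes first.** The investigator is to monitor "liver tests every 3 days following receipt of the prior laboratory results".
- **Testing may then be relaxed.** "The frequency of retesting can decrease to once a week or less if abnormalities stabilize and the patient is asymptomatic". Figure 1 footnote c repeats this sentence.
- **Stopping is mandatory.** "Patients must be discontinued from the study if an initial and repeat confirmatory laboratory tests meet any of the following criteria". One criterion is ALT or AST above 5 x ULN for at least 14 "consecutive days, at any time after initial confirmatory results". Section 5.8 item 16 carries the same criterion.

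After the End of Treatment Visit, when study drug has already been stopped, Appendix I uses almost the same relaxation: "The frequency of retesting can decrease to once a week or less if abnormalities stabilize and the subject is asymptomatic".

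**The concern.** A stopping rule based on duration works only if the interval between measurements is bounded. Here the relaxation covers the whole band from 3 to 8 x ULN, including the part above 5 x ULN where the 14-day clock runs. Its two conditions, stable values and no symptoms, describe the patient for whom the 14-day criterion is the only fixed liver limit: steady at 5 to 8 x ULN with normal bilirubin, so that neither the 8 x ULN criterion nor the bilirubin criterion applies.

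After the End of Treatment Visit an open-ended interval delays no stopping decision. During treatment it can. A site that follows the text could keep such a patient on study drug beyond the point at which stopping is required. What is at stake is patient safety; no endpoint, error rate or sample size depends on it.

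**Working it through.** The protocol gives no figure for this, so there is nothing to reproduce. The check is a timing calculation in whole days.

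**Inputs**
- Day 0 is the confirmatory sample above 5 x ULN, so the criterion can first be met on day 14 (Appendix I; Section 5.8 item 16).
- Default retest: 3 days after the prior result is received (Appendix I).
- Laboratory turnaround: "results will be reported back to the clinic within 72 hours" (Section 6.4.5), taken as 0 to 3 days.
- Relaxed interval T: weekly is the only value the text names. 14 and 28 days are my assumptions, used to show what an unbounded interval allows.

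**General bound.** The last draw before the criterion can be met falls on day 13 at the latest. The next falls on day 13 + T at the latest, so it is at most 13 + T − 14 = T − 1 days late.

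**Default cycle.** Spacing is turnaround plus 3 days, which is 3 to 6 days. Day 13 is reachable (for example 4 + 4 + 5 = 13), so the latest deciding draw is day 13 + 6 = 19, which is 5 days late.

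**Weekly.** The latest draw is day 13 + 7 = 20, 6 days late. Counted from day 0, the draws fall on days 7 and 14, and the decision is on time.

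**Longer than weekly.** Appendix I puts close testing first, so at least one further close draw is assumed. The last close draw L then lies between day 3 and day 13.
- T = 14: L + 14 = day 17 to 27.
- T = 28: L + 28 = day 31 to 41.

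| Retest pattern | Deciding draw (day) | Days late |
|---|---|---|
| Default, 3–6 days apart | 14–19 | 0–5 |
| Weekly | 14–20 | 0–6 |
| 2-weekly (assumed) | 17–27 | 3–13 |
| 4-weekly (assumed) | 31–41 | 17–27 |

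The result itself may take up to 3 more days in every row.

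**Does the visit schedule cap the delay?** Table 8 has ALT and AST at every visit from Visit 4 to Visit 12, and on-treatment visits are 4 to 12 weeks apart (Sections 3.1.4 and 3.1.5). Suppose the elevation is found at week 4. The confirmatory draw follows 0 to 6 days later (turnaround 0–3 plus repeat within 3 days). The week 8 visit then falls on day 28 − 6 = 22 to day 28, which is 8 to 14 days late (visit windows ignored). Where the next visit is 8 weeks away, it falls on day 56 − 6 = 50 to day 56, after even the 4-weekly deciding draw, and so does not shorten the delay.

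**The case against.** The strongest reply is that nothing here contradicts the stopping rule. The relaxation is optional and conditional, the 14-day criterion stands beside it and stays in force, and an investigator following a patient above 5 x ULN must test in order to apply it. For a material delay, a site would have to judge the values stable above 5 x ULN before day 14, choose an interval longer than weekly, and overlook the adjacent rule. Weekly testing costs at most one day more than the default cycle (day 20 against day 19). If a site went straight to 2-weekly draws counted from the confirmatory sample, the second draw would fall exactly on day 14.

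There are other safeguards. Every patient confirmed above 3 x ULN has an adverse event assessment, a physical examination, a risk-factor review and a specialised liver panel (Appendix I). A blinded committee adjudicates liver abnormalities (Section 6.4.15.2). The investigator and sponsor may stop drug at their discretion (Section 5.8 items 2 and 4), and the sponsor reviews safety data in real time (Section 1.4). Figure 1 itself is not shown, so it could hold a restriction that the text lacks.

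Much of this stands, and it narrows the risk. It does not close the gap. None of these safeguards, as described in the protocol, sets a retest interval or requires a draw near day 14. The committee's stated task is to judge the probability of drug-induced liver injury. A mandatory criterion exists so that stopping does not depend on discretion, and the visible footnote to Figure 1 carries the same unbounded wording.

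**Conclusion.** The point holds in a limited form. As written, a site may retest a patient on study drug, stable at 5 to 8 x ULN, less often than weekly, and so recognise the mandatory 14-day criterion late. The size depends on the interval chosen: at most 6 days for weekly testing, which is acceptable, and up to 13 or 27 days for the assumed 2-weekly or 4-weekly intervals. Delay is possible, not certain.

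Few patients should be affected. The protocol gives no rate, but ALT or AST above 3 x ULN is excluded at entry (Section 4.2 item 16), and Section 1.4 reports no liver-test imbalance in Phase III. The conclusion rests on the text of Appendix I and footnote c, because Figure 1 is not shown. The change is worth making as a cheap safety improvement; the efficacy analysis does not depend on it.

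**What to change.** Add one clause to the on-treatment branch of Appendix I and to Figure 1 footnote c:

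*While ALT or AST is >5 x ULN and the patient is on study drug, retest at least weekly, counted from the first confirmed value >5 x ULN; less frequent testing is allowed only at ≤5 x ULN or after study drug is stopped.*

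Draws then fall on days 7 and 14, so the criterion is decided on day 14 if that schedule is kept, and at most 6 days late for any other weekly alignment. The off-drug wording can stay as it is. The cost is an edit in two places and one or two extra central liver samples in a rare patient.
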